11.0 Criteria for Rescreening, Repeat Assessments, and Discontinuation

Repeat Assessments

Screening assessments can be repeated within the screening window under the same screening number with the exception of eligibility criteria related rating scales/questionnaires. Subject diagnosis confirmation will not be repeated.

Rescreening

Subjects who screen fail may be rescreened one time, under a new screening number. If a subject is rescreened, all screening assessments (with the exception of the diagnosis confirmation) must be repeated and the stability criteria timelines must be met.

Discontinuation

Subjects will be discontinued from the active treatment phase under the following circumstances:

1. Any psychosocial treatment changes
2. Suicide attempt
3. Missing 2 or more doses of study medication
4. Becoming pregnant
5. Developing a serious infectious disease
6. Have a change in stability criteria indicated in inclusion criteria #6
7. Subjects who require treatment with any excluded concomitant medications (See Attachment 2)

If subjects discontinue from the study, discontinuation assessments will be at the discretion of the

principal investigator.

A subject may withdraw from the study medication at any time at her own request, or may be withdrawn at any time at the discretion of the principal investigator for safety, behavioral, or administrative reasons.

12.0 Study Medication

Mifeprex tablets each contain 200 mg of mifepristone, a synthetic steroid with antiprogestational effects. The tablets are light yellow in color, cylindrical and biconvex, and are intended for oral administration only. The tablets include the inactive ingredients colloidal silica anhydrous, corn starch, povidone, microcrystalline cellulose, and magnesium stearate. Placebo tablets will look like mifepristone tablets, with matching shape, taste, and color. Mifepristone and matching placebo will be obtained from the manufacturer, Danco Laboratories in New York, NY. Study medication will be stored according to the details on the product label.

Dosing

The dosing used in this study is 600 mg by mouth once daily (see package insert for more information).

Compliance

Compliance will be assessed at each visit by direct questioning and medication count of unused medication and packaging to be returned at each visit. Adequate study medication dispensing records will be obtained.

13.0 Concomitant Medication

See Concomitant Medication Table Attachment 2

14.0 Adverse Events/Risks

For the purposes of collecting and evaluating all information found during this clinical study, an **adverse event** is any undesirable or unexpected experience that occurs after informed consent has been obtained without regard to the possibility of a causal relationship, and without regard to treatment group assignment. All adverse events will be documented and all serious adverse events will be reported following local Institutional Review Board (IRB) requirements.

For non-serious adverse events, research staff will question each subject and will document the occurrence and nature of presenting condition(s). Pre-existing condition(s) and any change in the pre-existing condition(s) will be documented and/or the occurrence and nature of any adverse event. Adverse events (AEs), especially those for which the relationship to study medication is not “unrelated,” will be followed up until they have returned to baseline status or stabilized at the discretion of the principal investigator. If after the follow-up period, return to baseline or stabilization cannot be established an explanation will be recorded in the source documentation.

The most common adverse events include:

- Nausea
- Vomiting

- Decreased appetite
- Diarrhea
- Fatigue
- Headache
- Dizziness
- Arthralgia
- Back pain
- High blood pressure

Females only:

- Endometrial hypertrophy
- Uterine cramping
- Vaginal bleeding

A **serious adverse event** is any adverse drug experience occurring at any dose that: results in death, is life threatening, results in inpatient hospitalization or prolongation of existing hospitalization, results in a persistent or significant disability/incapacity, or results in congenital anomaly/birth defect.

The following were considered serious adverse events in people with Cushing's syndrome and medical termination of pregnancy:

- Adrenal insufficiency
- Hypokalemia
- QT interval prolongation

It's not clear how frequently these serious adverse reactions may occur in an individual with BPD who does not have Cushing's syndrome and is not pregnant. This is because the vast majority of available safety data from clinical trials is for individuals with Cushing's syndrome or for women who used this medication for the termination of pregnancy and there is very little data available for people with neither condition.

Mifepristone has been used experimentally in research studies with patients with psychotic major depression. In these studies, mifepristone was well tolerated, and no serious side effects or medication-related problems were reported.

15.0 Data Safety Monitoring Board

The Indiana University Adult Psychiatry Data Safety Monitoring Board (DSMB) will be responsible for data and safety monitoring. DSMB is responsible for reviewing study procedures, adverse events, safety mailings (if applicable), enrollment, active subjects, and ongoing conduct of the research. The DSMB members can ask questions and make comments and/or recommendations. The IRB is notified of significant findings by way of the DSMB meeting minutes at the time of continuing review. An updated DSMB member list will be provided at the time of IRB continuing review or upon request.

Due to the small sample size and single site design of this protocol, there is not sufficient justification for conducting interim analyses to examine trends.

Data on the number of subjects enrolled and the number of adverse events will be reviewed by the DSMB at least **quarterly** and more frequently if needed. The resultant report will be issued to the IRB at the time of continuing review or more frequently by request.

Any unanticipated events will be immediately directed to the principal investigator who will follow the Indiana University IRB reporting procedures.

16.0 Statistical Considerations

Continuous variables will be summarized by treatment groups using descriptive statistics including mean, standard deviation, and range. Categorical variables will be summarized using frequency counts and percentages. Baseline clinical and demographic data will be compared between the two treatment groups to assess the effectiveness of the randomization. Dichotomous and ordinal variables will be examined using chi-square tests and continuous measures with Student's t-tests. Appropriate exact and non-parametric methods will be used as needed. The primary goal of this study will be to estimate the effect size for the treatment on the BPDSI total score. This will be done at each time point, as we are also interested in how the effect is sustained after active drug treatment is discontinued. We also will graph the trajectory of each subject over time. Supportive analyses will be based on the linear mixed effects model with a random subject effect for BPDSI with time, treatment and time by treatment interaction as covariates. The model parameters will be estimated using SAS MIXED procedure and the p-values for the comparisons of the differential treatment effects and 95% confidence interval for the treatment effect will be reported. The time by treatment interaction will be assessed to examine whether the active drug effect was changing over time. Secondary outcomes and serum cortisol levels will be examined similarly. Graphs, Pearson or Spearman correlations, and linear mixed models will be used to examine the relationship between serum cortisol levels and outcome measures. Due to the small sample size, covariates (type of abuse, age of abuse onset, abuse duration, diagnosis of MDD, diagnosis of PTSD) will be examined graphically. Safety analyses of this study will include summarized counts and rates per treatment group of the incidence of the adverse events. Incidences of selected adverse events from the two treatment arms will be compared using the Fisher's exact test on an exploratory basis.

Sample Size Justification: This is a pilot study designed to estimate effect sizes for a future randomized trial. It is recommended that a minimum of 12 subjects per group be used for this purpose based on estimating the precision of the meant treatment effect and variance (13).

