3.0 Specific Aims

Specific aim 1: to evaluate whether mifepristone will produce rapid symptom reduction after seven days of active treatment, as measured by Borderline Personality Disorder Severity Index (BPDSI) total score. Further, to evaluate whether seven days of mifepristone treatment will result in a durable improvement in symptoms persisting after active treatment discontinuation, as measured by Borderline Personality

Disorder Severity Index (BPDSI) total score.

Specific aim 2: to evaluate safety and tolerability of mifepristone

Specific aim 3: to assess cortisol levels as a potential biomarker of HPA-axis engagement.

Exploratory Aims: to assess clinical and demographic moderators of response to mifepristone, including childhood abuse characteristics (e.g., type of abuse, age of onset, duration) and comorbid psychiatric illnesses.

Outcome Measures: The primary outcome measures will be the Borderline Personality Disorder Severity Index (BPDSI) total score. With this measure, we will be able to investigate specifically the effect of mifepristone on BPD's entire psychopathologic spectrum. For inclusion, all subjects must demonstrate a minimum severity of a total score ≥ 3 on the CGI-S. Secondary outcomes will include the BPDSI symptom domain subscales, the Brief Psychiatric Rating Scale (BPRS), the self-report Borderline Checklist, the Symptom Checklist-90-Revised (SCL-90-R), improvement in metacognitive capacity, and the Clinical Global Impressions-Severity (CGI-S) and Clinical Global Impressions-Improvement (CGI-I) measures. Clinical assessments will be performed by trained raters, who will be blind to subjects' treatment condition.

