4.0 Study Design

This is a single site safety and proof of concept study conducted at the Indiana University Psychotic Disorders Program. Twenty four subjects with borderline personality disorder will be randomized 1:1 to double-blind treatment with oral mifepristone or matched placebo for duration of seven days, with a follow up period.

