21. Guy W. ECDEU assessment manual for psychopharmacology. Washington, DC: US Department of Health, Education, and Welfare;338:534-537. 1976.
22. Lobbestael, Arntz, Harkema-Schouten, & Bernstein (2009). Development and psychometric evaluation of a new assessment method for childhood maltreatment experiences: The Interview for Traumatic Events in Childhood (ITEC). *Child Abuse & Neglect*, 33, 505–1517.
24. Mifeprex [package insert]. Danco Laboratories, New York, NY, 2009..
25. Korlym [package insert]. Corcept Therapeutics Inc., Menlo Park, CA, 2000.

ATTACHMENT 1
Study Procedures Table

Visit	1	2	3	4	5	6
Day		0	4	7	14	28
Visit Window (days since last visit)		14-30	4	3	7	14
Informed Consent	X					
SCID I & II	X					
Medical History	X					
Demographics	X					
Physical Exam	X					
Vitals	X	X	X	X	X	X
Verification of Preg Prevention	X	X	X	X	X	X
ECG ^a	X	X	X	X	X ^b	X ^b
CGI-S/I	X ^c	X ^c		X	X	X
BPRS		X		X	X	X
BPDSI (90-day)	X					
BPDSI (7-day)		X		X	X	X
BPD Checklist		X		X	X	X
ITEC ^d	X					
SCL-90-R		X		X	X	X
IPII		X				X
CBC	X					
CMP	X	X		X	X	X
Serum Preg test (beta HCG)	X					
Blood Cortisol Level		X		X ^e	X ^e	X ^e
Biobank Blood Sample		X				X
Pharmacokinetics ^f				X		
Urine Pregnancy Test	X	X	X	X	X	X
Adverse Events			X	X	X	X
Concomitant Medication		X	X	X	X	X
Medication Dispensation		X				
Medication Accountability			X ^g	X		

a Triplicate tracings to be collected at least 1 minute apart

b Subsequent ECG tracings will be collected at V5 and V6 at the discretion of the principal investigator

c CGI-I will not be completed at Visits 1 or 2 as there is no "improvement" score at baseline.

d Clinician may use abbreviated version of form, at principal investigator's discretion

e Subsequent blood collection to occur at the exact time of day as the baseline value (+/- 30 minutes)

f Pharmacokinetic analysis will be completed based off of time of study drug from previous day.

g Study medication will be reviewed during this visit for compliance purposes. Study medication will not be returned or dispensed at this visit

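### The primary BPDSI effect size and the supportive mixed model name no adjustment for the Day 0 BPDSI, although it is collected at Visit 2

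*Combined protocol and SAP*

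**What the plan says.** Section 16.0 sets the aim: "The primary goal of this study will be to estimate the effect size for the treatment on the BPDSI total score". The estimate is to be made at every time point. The section does not say whether the effect is a post-treatment difference, a difference in change or a baseline-adjusted difference, and it names no SD to divide by.

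The supportive analysis is a "linear mixed effects model with a random subject effect for BPDSI with time, treatment and time by treatment interaction as covariates". The section does not state whether Day 0 is one of the response times. Baseline data are used only for a between-arm comparison that checks the randomisation. The covariates listed (abuse type, age at onset, duration, MDD, PTSD) omit baseline BPDSI and are to be examined only in graphs. The section adds: "Secondary outcomes and serum cortisol levels will be examined similarly".

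The Study Procedures Table in Attachment 1 schedules the 7-day BPDSI at Visits 2, 4, 5 and 6, which are Days 0, 7, 14 and 28. Section 4.0 gives the design as "Twenty four subjects with borderline personality disorder will be randomized 1:1" and names no stratification factor. The purpose of the sample size, again in Section 16.0, is: "This is a pilot study designed to estimate effect sizes for a future randomized trial".

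**The concern.** The supportive model can be read in two ways.

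- **Day 0 is a response level.** The plan's "We also will graph the trajectory of each subject over time" and the aim in Section 3.0, "to evaluate whether mifepristone will produce rapid symptom reduction after seven days of active treatment", point this way. With the arm means left free at Day 0 and complete data, the contrasts against Day 0 are plain change-score differences.
- **Day 0 is left out.** The contrasts are then plain post-treatment differences.

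Neither reading removes a chance Day 0 difference. The post-treatment difference under-corrects for it. The change score over-corrects, as long as the correlation times the SD ratio is below 1. The primary effect size has no formula at all, so it could follow either route.

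Unbiasedness over repeated randomisations is not in question. At stake are precision and the error in this one trial, given the imbalance it happens to have. A single estimate from 24 subjects is to be carried into the planning of the next trial, so both matter.

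**Working it through.** **Inputs from the documents.** 24 subjects at 1:1 (Section 4.0); at least 12 per group and a 95% interval (Section 16.0); 7-day BPDSI at Days 0, 7, 14 and 28 (Attachment 1). The plan's own figures agree: 2 × 12 = 24. The 12 per group is a cited rule of thumb without power, effect size or SD, so there is no power calculation to reproduce.

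**Assumptions (not in the documents).** Complete data; categorical time; correlation r between Day 0 and follow-up of 0.3, 0.5 or 0.7; k = follow-up SD / Day 0 SD of 0.8, 1.0 or 1.3, the same in both arms. Results are in Day 0 SDs.

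**Chance imbalance.** The SD of the Day 0 difference is √(2/12) = 0.408. P(|difference| ≥ 0.5) = 2 × (1 − Φ(0.5/0.408)) = 0.22. For 0.25 SD the probability is 0.54.

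**95% CI half-widths.**
- Post-treatment: 2.074 × 0.408 × k
- Change: 2.074 × 0.408 × √(1 + k² − 2rk)
- ANCOVA: 2.080 × 0.408 × k × √((1 − r²)(1 + 1/20)). The critical value has 21 rather than 22 degrees of freedom, and 1/20 is the average cost of estimating the slope.

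| k | r | Post | Change | ANCOVA | Gain over better | Gain over worse |
|---|---|---|---|---|---|---|
| 1.0 | 0.3 | 0.847 | 1.002 | 0.830 | 0.017 | 0.17 |
| 1.0 | 0.5 | 0.847 | 0.847 | 0.753 | 0.093 | 0.09 |
| 1.0 | 0.7 | 0.847 | 0.656 | 0.621 | 0.035 | 0.23 |
| 0.8 | 0.3 | 0.677 | 0.912 | 0.664 | 0.013 | 0.25 |
| 0.8 | 0.5 | 0.677 | 0.776 | 0.603 | 0.075 | 0.17 |
| 0.8 | 0.7 | 0.677 | 0.611 | 0.497 | 0.114 | 0.18 |
| 1.3 | 0.3 | 1.101 | 1.170 | 1.079 | 0.022 | 0.09 |
| 1.3 | 0.5 | 1.101 | 0.998 | 0.979 | 0.019 | 0.12 |
| 1.3 | 0.7 | 1.101 | 0.790 | 0.808 | −0.018 | 0.29 |

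(Gains over the better option are from unrounded values.)

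**In subjects, at k = 1.** The equivalent N against the better unadjusted option is 24 × min(1, 2(1 − r)) / ((1 − r²) × 1.05) = 25.1, 30.5 and 26.9. That is about 1, 6 and 3 extra subjects.

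**Shift for a given imbalance d.** The post-treatment estimate moves by rkd and the change estimate by (rk − 1)d. At k = 1 and d = 0.5, the post-treatment estimate moves by 0.15, 0.25 or 0.35 SD towards the imbalance. The change estimate moves by 0.35, 0.25 or 0.15 SD the other way. The two estimates therefore differ by d, here 0.5 SD.

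**Standardiser, at k = 1.** Dividing by the SD of change instead of the Day 0 SD multiplies the effect size by 1/√(2(1 − r)) = 0.85, 1.00 or 1.29.

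**Simulation check (40,000 trials per case).** At k = 1 the SD of the ANCOVA estimate was 0.399, 0.363 and 0.300. In all nine cases its slope on the Day 0 difference was within 0.01 of zero, and interval coverage was 0.948 to 0.952. A four-visit model with a common Day 0 mean and only a random subject effect (1,500 trials per case) gave an SD of the Day 7 estimate within 0.013 of ANCOVA. However, in a two-visit approximation of that model at k = 1.3, between 0.12 and 0.24 of the Day 0 imbalance remained in the estimate.

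**The case against.** The strongest reply is that this is a preference for efficiency. Nothing in Section 16.0 is shown to be wrong, no go/no-go threshold hangs on the effect size, and the mixed-model p-values are only supportive. That is true, and it limits the weight of the point.

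The size also depends on assumed values. At k = 1, ANCOVA is slightly wider than the better unadjusted option at r = 0 (0.870 against 0.847), r = 0.1 (0.866) and r = 0.2 (0.852). It gains only 0.013 at r = 0.8 and nothing at r = 0.9. At k = 1.3 it loses 0.025 at r = 0.1 and 0.030 at r = 0. Low correlations cannot be excluded for a modified 7-day scale. These losses stand, but none exceeds 0.03 SD.

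The two shifts run in opposite directions only while rk is below 1. This holds in all nine cases. At k = 1.3 and r = 0.7, however, the change-score shift for a 0.5 SD imbalance is only −0.045 SD, and at r = 0.8 it becomes +0.02 SD.

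It can also be said that baseline already enters the supportive model if Day 0 is a response. The text does not settle this. If it is so, the contrast is still an unadjusted change score, and the primary effect size still has no formula.

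Two narrower points are fair. The standardising SD is a separate omission and adds no weight to the case for adjustment. The calculations do not cover cortisol: the background describes a 2- to 3-fold rise under mifepristone, so the variance at Day 7 may differ between arms.

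**Conclusion.** The concern holds. The plan names no Day 0 BPDSI adjustment in either analysis, and the matching baseline value is already collected. The unadjusted estimates are unbiased on average and their intervals are valid, so the cost is precision and sensitivity to chance imbalance.

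The gain over the better unadjusted option is modest. Over the nine assumed cases, adjustment changes the half-width by between 0.02 SD wider and 0.11 SD narrower. Against the worse option it is 0.09 to 0.29 SD narrower, or 8% to 27%. Since r and k are unknown before the data are in, adjustment is the safer choice: it stays close to the better option or beats it. The change should be made, but its absence does not invalidate the analysis.

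**What to change.** In Section 16.0, define the BPDSI effects at Days 7, 14 and 28 as baseline-adjusted mean differences with 95% CIs, and choose one of:

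- **(a)** ANCOVA at each visit, or a mixed model of the post-baseline visits with the Visit 2 7-day BPDSI and its interaction with time; or
- **(b)** the planned mixed model with Day 0 as a response level, categorical time and a common Day 0 mean across arms. The Day 0 and follow-up variances must be allowed to differ, because a random subject effect alone can leave part of the imbalance in the estimate.

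Use the 7-day score at Visit 2 as the baseline. The 90-day version at Visit 1 has another recall period and item scale. Standardise by one prespecified SD, for example the pooled Day 0 SD.

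Apply the same rule to secondary scales and cortisol where a Visit 2 value exists, at the visits where each is measured. IPII-based measures have only Visits 2 and 6. For cortisol, allow for different variances by arm. CGI-I is outside the rule, since "CGI-I will not be completed at Visits 1 or 2" (Attachment 1, footnote c).

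The cost is a few lines of text and one degree of freedom per visit. In the least favourable of the nine cases the interval half-width is 0.02 SD wider than with change scores. No new data, visits or subjects are needed.

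### The supportive mixed model's only within-subject term is a random subject effect, so every between-visit treatment contrast gets the same SE; intervals for change are misstated unless BPDSI variances and correlations are nearly equal across Days 0, 7, 14 and 28

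*Combined protocol and SAP*

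**What the plan says.** Section 16.0 puts estimation first: "The primary goal of this study will be to estimate the effect size for the treatment on the BPDSI total score", at each time point. The mixed model ranks below that: "Supportive analyses will be based on the linear mixed effects model". It is described as a "linear mixed effects model with a random subject effect for BPDSI with time, treatment and time by treatment interaction as covariates", and "The model parameters will be estimated using SAS MIXED procedure". From it the plan promises p-values, and a "95% confidence interval for the treatment effect will be reported". It adds: "The time by treatment interaction will be assessed to examine whether the active drug effect was changing over time". Secondary outcomes and serum cortisol are to be handled in the same way.

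The section does not state a residual covariance structure, a robust SE, a degrees-of-freedom method, whether time is categorical or continuous, or whether Day 0 is a response or a covariate. It does not define the reported treatment effect as a change from Day 0.

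Section 4.0 sets the size: "Twenty four subjects with borderline personality disorder will be randomized 1:1". Attachment 1 schedules the 7-day BPDSI at Visits 2, 4, 5 and 6 (Days 0, 7, 14 and 28). The row that begins "Visit Window (days since last visit" gives the spacing: 4 + 3 = 7 days from Visit 2 to Visit 4, then 7, then 14.

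**The concern.** A random subject effect with independent residuals is compound symmetry: one variance at every visit and one correlation for every pair of visits. The visits here are unequally spaced and the instrument looks back 7 days, so Days 0 and 7 may well correlate more than Days 0 and 28. The model cannot represent that. It averages the within-subject variation and applies one SE to every contrast between visits.

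Contrasts between visits are where Specific Aim 1 lies. It asks about rapid improvement by Day 7 and about persistence after the drug stops, and the interaction test compares visits by construction. If the averaged SE is wrong for those contrasts, the supportive intervals and p-values passed on to the planning of a later trial are wrong too.

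**Working it through.** **Inputs from the documents.** 12 per arm (Section 16.0) and 1:1 allocation of 24 (Section 4.0): 2 × 12 = 24, which reproduces the only stated figure that bears on this point. Four BPDSI visits at Days 0, 7, 14 and 28 (Attachment 1). Two-sided 5%, implied by the 95% interval.

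**Assumed, because the documents are silent.** SD of 1 at every visit unless stated, complete data, and a range of correlation structures.

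**Formulas.** Let V be the true 4 × 4 covariance and P the matrix that centres over the four visits.
- Residual variance the model settles on: s² = trace(PVP)/3. With unit variances this is 1 − r̄, where r̄ is the mean of the six pairwise correlations.
- Model SE for the treatment difference in any between-visit change: √(2s² × 2/12).
- True SE for change from Day 0 to Day k: √((Vₖₖ + V₀₀ − 2V₀ₖ) × 2/12).

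**Worked case: correlation 0.8 per 7 days, decaying with time.**
- Day 0 with Days 7, 14, 28: 0.8, 0.64, 0.4096. Day 7 with Days 14, 28: 0.8, 0.512. Day 14 with Day 28: 0.64.
- Sum 3.8016, mean 0.6336, so s² = 0.3664.
- Model SE: √(2 × 0.3664 × 2/12) = 0.349 SD.
- True SE, Day 7 − Day 0: √(2 × 0.2 × 2/12) = 0.258. Ratio 1.35.
- True SE, Day 28 − Day 0: √(2 × 0.5904 × 2/12) = 0.444. Ratio 0.79.
- Day 28 − Day 7: ratio √(0.3664/0.488) = 0.87.

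**Range.** Entries are model SE / true SE, with simulated type I error of the nominal 5% test in brackets (at least 20,000 null trials per row; t with 22 × 3 = 66 df).

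| Assumed structure | Day 7 − Day 0 | Day 28 − Day 0 |
|---|---|---|
| Decay, 0.9 per 7 days | 1.41 (1%) | 0.76 (13-14%) |
| Decay, 0.8 | 1.35 (1%) | 0.79 (12-13%) |
| Decay, 0.7 | 1.30 (1%) | 0.82 (11%) |
| Decay, 0.5 | 1.20 (2%) | 0.88 (8-9%) |
| Stable subject part 0.6, remainder decaying at 0.3 | 1.11 (3%) | 0.93 (7%) |
| Equal correlation, equal variance | 1.00 (5%) | 1.00 (5%) |
| Day 0 correlates 0.5 with later visits, later visits 0.7 with each other | 0.89 (8%) | 0.89 (8%) |
| Equal correlation 0.6, Day 7 SD 1.4 times the others | 0.90 (7-8%) | 1.14 (3%) |

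Day 14 − Day 0 is close to correct in the five decay rows (ratios 0.97 to 1.02).

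**Other quantities.**
- Overall interaction test, time categorical, 3 and 66 df: about 5-7% across the decay rows (6.4-6.6% at 0.7-0.8). If time were entered as a straight line, the slope-by-treatment test would reject about 13-14% at 0.7-0.8.
- Treatment difference at a single visit: coverage 95.2-96.0% in the decay rows. With Day 7 SD 1.4 times the others, Day 7 coverage falls to 89.6%.
- Contrast-specific variance with 22 df, which is what an unstructured covariance gives with complete data: coverage 94.7-95.2% for change from Day 0 in every row.
- Cortisol: the background section expects a 2- to 3-fold rise in central cortisol on drug, so equal variance on and off drug is doubtful. If the Day 7 SD were double the others (assumed), the pooled variance would be (1 + 4 + 1 + 1)/4 = 1.75 against a true 4. The single-visit Day 7 SE would then be √(1.75/4) = 0.66 of its true value.

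**The case against.** A reader might infer that the plan's intervals are definitely too wide for Day 7 and too narrow for Day 28. The documents do not support that. It requires correlation that decays with time and roughly equal variances, and they give neither. Truly equal correlation removes the error. A weaker baseline correlation makes both intervals too narrow. A larger Day 7 SD reverses the pattern. Even within the decay family, a stable subject component shrinks the error to 11% at Day 7 and 7% at Day 28.

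A reader might also infer that the main result is compromised. It is not. The model is supportive, no success threshold hangs on it, and with complete balanced data the point estimates are the same under either covariance. The plan never names change from Day 0 as the contrast to be reported, and a difference at one visit is essentially unaffected when variances are equal. The one cross-visit test it does name, the interaction, is only mildly inflated if time is categorical. The missing degrees-of-freedom method is not a separate demonstrated error: 66 df is right for within-subject contrasts if equal correlation holds and data are complete. Nor does the text exclude a residual structure; it states none.

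All of this limits the point without removing it. The structures that change the direction also leave the intervals wrong, and only near-equal variances and correlations make the model right. Aim 1 asks about improvement and its persistence, so change contrasts are a natural use of this model.

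**Conclusion.** The concern holds in conditional form. As written, the model gives all between-visit treatment contrasts one SE, and nothing in the documents justifies the assumption behind it. How far the intervals are off, and in which direction, depends on SDs and correlations that the documents do not give. The 11-41% overstatement at Day 7 and 7-24% understatement at Day 28 rest on decaying correlation, equal variances, 12 per arm and no missing visits. The consequence is confined to supportive SEs, intervals and p-values for change; the primary effect sizes stand. The change is worth making before analysis because a method that holds its level across all the structures examined is available at little cost.

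**What to change.** In PROC MIXED, replace the random subject effect with `REPEATED visit / SUBJECT=id TYPE=UN` and use `DDFM=KR`. State that time is categorical, that Day 0 is a response, and which contrasts will be reported. Pre-specify a fallback for non-convergence: spatial power on study day, preferably with a random subject effect or heterogeneous variances. Use the same structure for the secondary outcomes and cortisol.

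The cost is about two lines of code and a few sentences in Section 16.0. If equal correlation truly holds, the critical value rises from 1.997 (66 df) to 2.074 (22 df), and 2.074/1.997 = 1.04, so intervals are about 4% wider. The unstructured matrix needs ten parameters (4 variances and 6 covariances) from 24 subjects. Its behaviour with missing visits was not examined here, which is why the fallback should be fixed in advance.
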